Participant's LY900014 dose will be reviewed using the InPen report. The investigator should confirm that the InPen report has been received before each study visit. Additionally, the investigator should confirm that the InPen report aligns with the clinical management of the participant. Based on these reports, insulin doses, ICR, ISF, and DIA will be adjusted as needed to reach the study specified glucose target (Sections 4.3.1 and 4.3.2).

Maintenance Period, Day 36 to Day 46

The maintenance period starts following Visit 13. Continuous glucose monitoring data collected during the maintenance period will be used as endpoint CGM data.

During the maintenance period, the investigator may not adjust the dose of insulin degludec, ICR, ISF, or DIA unless for safety reasons.

During the maintenance period from Day 36 to Day 45, participants are required every day to enter the following data into the Dexcom mobile app

- meal start time for breakfast, lunch, and dinner
- insulin degludec dose

Investigator staff should check CLARITY to ensure that participants are entering these data during the maintenance period.

Visit 14 (Day 46)

At Visit 14, participants will return to their non-study rapid-acting insulin analog regimen. Participants may decide to continue to administer degludec in the morning or switch to their pre-study dosing schedule. The investigator will determine basal and prandial insulin doses.

At Visit 14, participants will return to the personal CGM system that they were using before the study began. Participants should be reminded before Visit 14 that they will need to bring their personal CGM system to Visit 14.

Transcribing Data into the eCRF from Visit 3 to Visit 14

At every visit from Visit 3 to Visit 14 inclusive, the investigator should transcribe the following data from the day before the visit into the eCRF:

- ICR
- ISF
- DIA

Transcribing Data into the eCRF for Visit 3 and Visit 14 only

In addition to the ICR, ISF, and DIA, the investigator should transcribe the Humalog dose at Visit 3 (data from Day -10 to Day -1) and the LY900014 dose at Visit 14 (data from Day 36 to Day 45).

Safety Follow-up, Visit 801

All randomized participants who completed the treatment period should have a safety follow-up visit approximately 1 week after Visit 14.

Early Termination visit, ET Visit

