8.2.6. Hypoglycemia

Participants will be trained about signs and symptoms of hypoglycemia, how to treat hypoglycemia, and how to discuss hypoglycemic events with investigators.

Hypoglycemia will be described using the following definitions:

- **Level 1:** Glucose <70 mg/dL (3.9 mmol/L) and \geq 54 mg/dL (3.0 mmol/L)
- **Level 2:** Glucose <54 mg/dL (3.0 mmol/L)
- **Level 3: Severe hypoglycemia:**

A severe event characterized by altered mental and/or physical status requiring assistance for treatment of hypoglycemia. Participants have altered mental status and cannot assist in their own care, may be semiconscious or unconscious, or experience coma with or without seizures, and require assistance of another person to actively administer carbohydrate, glucagon, or other resuscitative actions. Glucose measurements may not be available during such an event, but neurological recovery attributable to the restoration of blood glucose concentration to normal is considered sufficient evidence that the event was induced by a low blood glucose concentration.

- The determination of a hypoglycemic event as an episode of severe hypoglycemia, as defined above, is made by the investigator based on the medical need of the participant to have required assistance and is not predicated on the report of a participant simply having received assistance.
- All episodes of severe hypoglycemia must be reported as SAEs on the AE eCRF page and on the SAE eCRF page.

Any events of severe hypoglycemia categorized as level 3 per the evaluation of investigators will be collected from ICF signing to Visit 801.

Episodes of hypoglycemia categorized as level 1 or level 2 will be analyzed based on data from the CGM sensor session. Therefore, level 1 and level 2 hypoglycemic events do not need to be reported as an AE.

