9.4.5. Other Safety Analyses

Safety measures will include AEs, vital signs, and treatment exposure. Events that are newly reported after the first dose of IP used or reported to worsen in severity from baseline (details will be described in SAP) will be considered TEAEs.

Analyses of AEs will be descriptive and include all data collected during the treatment period. AEs during the lead-in period and the safety follow-up period will be provided in a listing.

Serious AEs, AEs reported as the reason for discontinuation from the IP or study, and TEAEs will be summarized in tables using the Medical Dictionary for Regulatory Activities (MedDRA) Preferred Term sorted by decreasing frequency. Treatment-emergent AEs will also be summarized by preferred term sorted by decreasing frequency within the SOC for all TEAEs and by maximum severity. For events that are gender-specific (as defined by MedDRA), the denominator and computation of the percentage will include only patients from the given gender. The number and proportion of patients with at least 1 event for each type of event will also be summarized.

In addition, time in hypoglycemic ranges will be assessed by CGM analyses.

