- Any clinically significant abnormal laboratory findings or other abnormal safety assessments which are associated with the underlying disease, unless judged by the investigator to be more severe than expected for the participant's condition. Such a finding includes an episode considered to be related to hypoglycemia categorized as either level 1 or level 2 based on plasma glucose levels.
 - Level 1: <70 mg/dL (3.9 mmol/L) and glucose \geq 54 mg/dL (3.0 mmol/L)
 - Level 2: <54 mg/dL (3.0 mmol/L)
- The disease/disorder being studied or expected progression, signs, or symptoms of the disease/disorder being studied, unless more severe than expected for the participant's condition.
- Medical or surgical procedure (for example, endoscopy and appendectomy): the condition that leads to the procedure is the AE.
- Situations in which an untoward medical occurrence did not occur (social and/or convenience admission to a hospital).
- Anticipated day-to-day fluctuations of pre-existing disease(s) or condition(s) present or detected at the start of the study that do not worsen.

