Lead-in Period	Enrolled Population	Listing: All AE including SAEs and discontinuation due to AE	N/A	Humalog
Treatment Period (Titration and Maintenance periods)	Treated Population	AE overview; TEAE by SOC and by PT;; SAE; discontinuation due to AE	Yes	LY900014
Treatment Period (Titration and Maintenance periods) and Safety Follow-up Period	Treated Population	AE overview; TEAE by SOC; SAE; discontinuation from study due to AE;	All data regardless of IP use	LY900014

Abbreviations: AE = adverse event; IP = investigational product; N/A = not applicable/available; PT = preferred term; SAE = serious adverse event; SOC = system organ class; TEAE = treatment-emergent adverse event.

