6.10.3. Hypoglycemic Events and Other Adverse Events

The analysis plans for the following AEs are discussed in Section 6.10.3.1:

- hypoglycemia
- injection site reaction

These AE analyses will be similar to the TEAE analyses, refer to [Table ITSZ.6.3](#) for the requirement of analysis data for a specific analysis period.

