6.13. CGM Analyses

The analyses described in Section 6.13 will include data collected from first dose of Humalog used during the lead-in period to the last IP used during the treatment period, excluding data (if any) that are collected while patients are temporarily off Humalog or IP.

All CGM outcome variables will only be derived for Visit 3 (baseline) and Visit 14 (endpoint) based upon the CGM data collected from valid CGM days, excluding data (if any) that are collected while patients are temporarily off Humalog during the lead-in period or temporarily off IP during the maintenance period. A valid CGM day to be counted into the calculation for a visit must have at least 70% of the total measures that are supposed to be obtained.

[Table ITSZ.6.5](#) lists all numerical measures for CGM data.

To ensure that the CGM outcome variables are only calculated from CGM session days with sufficient data within the 24-hour, daytime (0600 hours to midnight), or nighttime (midnight to 0600 hours) periods, the following criteria will be used to determine a valid CGM session day to be counted into the calculation for a visit: minimum number of measures per day – at least 70% of the total measures that are supposed to be obtained, i.e., 70% of the 288 measures for the 24-hour period;

Similarly, for the by-meal outcome variables, the following criteria will be used to determine a valid CGM session day for a visit: minimum number of measures per day – at least 70% of the

total measures that are supposed to be obtained. For example, 70% of the 24 measures for the $iAUC_{0-2hr}$ after breakfast.

The definition and derivation of these variables are described in detail in [Appendix 1](#).

Table ITSZ.6.5. Outcome Measures of CGM Data

Category	Endpoints	24-Hour	Daytime ^a	Nighttime ^b	By Meal ^c
Efficacy Endpoint: Glucose in the Target Ranges					
	Duration (in minutes) and percentage of time with sensor glucose values within target range 70 to 180 mg/dL [3.9 and 10.0 mmol/L], both inclusive (Primary Efficacy Endpoint)	X	X	X	
Efficacy Endpoint: Incremental AUCs (iAUCs) (after the start of meals)					
	$iAUC_{0-1hr}$				X
	$iAUC_{0-2hr}$				X
	$iAUC_{0-3hr}$				X
	$iAUC_{0-4hr}$				X
Efficacy Endpoint: Mean Glucose Excursions (after the start of meals) ^d					
	mean sensor glucose excursions 0 to 1 hour				X
	mean sensor glucose excursions 0 to 2 hour				X
	mean sensor glucose excursions 0 to 3 hour				X
	mean sensor glucose excursions 0 to 4 hour				X

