The proportion of patients who have achieved the guidance (Battelino 2019) recommended CGM targets of glycemic control (Table ITSZ.6.6) during the lead in period (baseline) and the maintenance period (endpoint) will be summarized.

Table ITSZ.6.6. Guidance Recommended CGM Targets of Glycemic Control

Percentage of time with sensor glucose (24-hour)	Guidance Recommendation
target range	
70-180 mg/d.L (3.9-10.0 mmol/L, both inclusive)	>70%
hypoglycemia range	
<54 mg/dL (3.0 mmol/L)	<1%
hyperglycemia range	
>250 mg/dL (13.9 mmol/L)	<5%

Other than that, all continuous variables (actual and change from baseline, if applicable) will be analyzed by using the ANCOVA defined in Section 6.1.

In addition, the following standardized glucose summary reports from the ambulatory glucose profile (AGP) will be generated, based upon all the observed CGM data during the lead in period and the maintenance period, regardless of whether they are collected on valid CGM days:

- 24-hour period at individual patient level
- 24-hour period at the treatment level
- 0 to 4 hours relative to meal starting time, excluding data collected after the next meal event (if any is captured within the interval) at the treatment level
- 0 to 4 hours relative to meal starting time, by meal (breakfast, lunch, and dinner) and by infusion set wear day excluding data collected after the next meal event

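### Level 1 and Level 2 hypoglycemia during the 35-day titration period (76% of treatment days), including in anyone who leaves during it, is not tabulated in any planned analysis

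*SAP*

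**What the plan says.** **Source of Level 1/2 data.** Protocol 8.2.6 takes Level 1 and Level 2 episodes from the CGM sensor session and draws the consequence: "Therefore, level 1 and level 2 hypoglycemic events do not need to be reported as an AE". Protocol 10.3.1 lists among findings that are normally not adverse events "an episode considered to be related to hypoglycemia categorized as either level 1 or level 2 based on plasma glucose levels", with an exception for findings more severe than expected. SAP 6.10.3.1 sends the Level 1/2 analysis to SAP 6.13. Protocol 9.4.5, on safety analyses, adds: "In addition, time in hypoglycemic ranges will be assessed by CGM analyses".

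**Period covered.** SAP 6.13 states: "All CGM outcome variables will only be derived for Visit 3 (baseline) and Visit 14 (endpoint". SAP 6.1, SAP Appendix 1 (9.1) and protocol 9.4.1 set the same limit. Protocol 4.1.1 makes the lead-in the CGM baseline and says of the other end: "Continuous glucose monitoring data collected during the maintenance period will be used as endpoint CGM data". The ambulatory glucose profile (AGP) reports in SAP 6.13 use "all the observed CGM data during the lead in period and the maintenance period".

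**Wider wording in the same SAP.** The first sentence of 6.13 says its analyses include data from the first lead-in Humalog dose to the last study drug dose in the treatment period. The last line of Appendix 1, 9.1 likewise admits readings taken on study drug during the treatment period.

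**Who is included.** The CGM row of Table ITSZ.6.2 needs both a baseline and a post-baseline value. SAP 6.3 restricts the ANCOVA to completers and leaves missing CGM data unaddressed. Under protocol 4.1.1, permanently stopping study drug means leaving the study.

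**The concern.** The rationale in protocol 2.1 is that LY900014 may permit more aggressive mealtime dosing without more late post-meal lows. Protocol 4.3.2 and 4.3.3 have investigators adjust prandial settings and degludec about twice a week during titration, so this is when doses are being pushed. Participants wear the sensor throughout. Table ITSZ.6.5 labels time in the hypoglycemic ranges a safety endpoint, yet the planned tabulation starts only after dosing is fixed.

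As written, any statement about Level 1/2 hypoglycemia under the scheme would describe the last 11 days, in people who stayed to the end, at settings that may already have been reduced because of lows. A reader of the report could take it to describe the whole scheme.

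**Working it through.** **1. The plan's own figure.** SAP 5.2 gives SD 12%, 30 evaluable participants, 34 assigned at 10% dropout, and about 80% probability that the 95% CI half-width is within 4.93%.

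- P(t(0.975, 29) × s/√30 ≤ 4.93), with 29 × s²/12² distributed as chi-square on 29 df, is 0.799. The 80th-percentile half-width is 4.932.
- 30/0.90 = 33.3, which rounds up to 34.

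Both figures reproduce. The point does not depend on them; it uses only the 34 and the 30.

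**2. Where could a Level 1/2 low in titration appear?**

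| Planned output | Covers titration? | Carries Level 1/2? |
|---|---|---|
| Time <54, 54-69, <70 mg/dL (Table ITSZ.6.5) | No | Yes |
| CGM target attainment (Table ITSZ.6.6) | No | <54 mg/dL only |
| AGP reports (SAP 6.13) | No | As a glucose profile |
| Severe hypoglycemia (Table ITSZ.6.4) | Yes | No, Level 3 only |
| Adverse event tables (Table ITSZ.6.3) | Yes | Only by exception |
| Disposition and reasons for discontinuation (SAP 6.5) | Yes | A reason, no glucose data |
| Episode duration (Appendix 1, 9.9) | No period stated | A formula with no table |

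No row both covers titration and routinely carries Level 1/2 data.

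**3. Does the wider wording close the gap?** No. The first sentence of 6.13 sets a data scope, and the next, more specific sentence limits derivation to two visits. No variable, period or display is defined for titration. The two sentences are in tension, but the wider one does not supply coverage.

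**4. Share of treatment.** Inputs are 35 titration days and 11 maintenance days (SAP 5.1).

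- Titration: 35/(35 + 11) = 35/46 = 76.1%. Maintenance: 11/46 = 23.9%.
- Counting calendar Days 0-35 of 0-46: 36/47 = 76.6%.
- At the visit-window extremes: 34/49 = 69.4% (Visit 13 on Day 34, Visit 14 on Day 49) and 37/46 = 80.4% (Visit 13 on Day 37, Visit 14 on Day 46).
- At 288 readings a day (SAP 6.13), 35 × 288 = 10,080 of 46 × 288 = 13,248 scheduled readings per completer enter no hypoglycemia table.

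**5. Participants.** 34 − 30 = 4, and 4/34 = 11.8%. The documents do not say when these participants would leave. If all four left between Day 1 and Day 35 (an assumption), on-treatment participant-days would be 30 × 46 + 4 × 1 = 1,384 to 30 × 46 + 4 × 35 = 1,520. Those tabulated would be 30 × 11 = 330, or 23.8% to 21.7%.

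**6. Sensitivity, on assumed rates only.** Suppose a completer spends 0.5% of maintenance time below 54 mg/dL and r% of titration time. The whole-treatment figure is (35r + 11 × 0.5)/46:

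- r = 0.3 gives 16.0/46 = 0.35%
- r = 0.5 gives 0.50%, no change
- r = 1.5 gives 58.0/46 = 1.26%

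None of these rates comes from the documents. They show only that the maintenance figure does not determine the whole-treatment figure.

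**The case against.** The strongest reply is that the limit is deliberate and consistent. The objectives in both documents define time <54 mg/dL as an exploratory measure in the maintenance period, protocol 9.4.1 repeats the two-visit limit, and the study is an exploratory pilot. Investigators review CGM data at every titration visit and Level 3 events are collected throughout. SAP 6.13 also derives post-meal hypoglycemia at held settings, which is closer to the rationale than whole-day figures from a period when basal doses are changing too. All of this stands. It justifies keeping the endpoints and shows that participants are monitored. It does not produce a reported Level 1/2 result for titration, and general permission for additional exploratory analyses does not specify one.

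Four stronger readings are tempting, and the documents do not support them:

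- *SAP 6.10.3 contradicts 6.13.* It says "These AE analyses will be similar to the TEAE analyses" and points to Table ITSZ.6.3, whose rows include "Treatment Period (Titration and Maintenance periods". That text governs recorded adverse events. Level 1/2 episodes are not routinely recorded as such, and 6.10.3.1 sends them to 6.13.
- *Early leavers disappear altogether.* SAP 6.5 summarizes and lists reasons for discontinuation, and protocol 7.2 names safety as a ground for investigator withdrawal. Only their on-treatment Level 1/2 data are lost. Protocol 7.1 expects discontinuation to be uncommon.
- *Hypoglycemia will be understated.* It could be, if lows led to dose cuts before maintenance. It could be overstated if doses were highest at the end.
- *The <1% target would be missed over the whole treatment period.* That target is specified for lead-in and maintenance. Extending it to titration would create a different endpoint.

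**Conclusion.** The gap is real and should be closed. It concerns reporting and does not show that participants are inadequately watched. Its certain size is 35 of 46 scheduled treatment days (76%; about 69% to 80% across visit windows). Up to about 4 of 34 participants could also contribute nothing on treatment, if all the planned dropouts left during titration. The effect on the hypoglycemia estimate cannot be derived from the documents in size or direction, and it is nil if titration and early leavers resemble maintenance. The conclusion rests on reading the two-visit restriction as controlling over the broader sentences in 6.13 and Appendix 1, 9.1. That is the natural reading, because no titration output is defined anywhere.

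**What to change.** Leave the maintenance endpoints and the ANCOVA unchanged. In SAP 6.10.3.1, 6.13 and Table ITSZ.6.2, add one descriptive safety summary without a test:

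- **Measures:** minutes and percentage of time <54, 54-69 and <70 mg/dL, for 24 hours, daytime and nighttime, by the derivation already in Appendix 1, 9.2.
- **Periods:** titration by week, and first dose to last dose of study drug. The second matches the period already used for severe hypoglycemia.
- **Rules:** the same valid-day and on-drug rules as the endpoint, so that the figures are comparable.
- **Participants:** every treated participant with at least one valid CGM day after first dose, plus a listing of early leavers with their time <54 mg/dL.

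Reword the opening sentence of 6.13 and the last line of Appendix 1, 9.1 so that scope and derivation agree. Record the reason for going beyond the two-visit limit in protocol 9.4.1. Protocol 9.4 lets a change that leaves the principal features intact be justified in the SAP or study report without an amendment. If the sponsor declines, the SAP and report should say that Level 1/2 hypoglycemia in titration is not analyzed.

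The cost is one more run of an existing derivation and one extra table, with no new procedure for participants. The table has limits. It reflects changing prandial and basal doses, is not steady state, and does not isolate late post-meal lows. By-meal results are not requested, because the Schedule of Activities requires meal times in the Dexcom app only for Days -10 to -1 and 36 to 45. The documents do not say whether titration CGM files reach the sponsor's database; the fix assumes that they can be extracted from the same system.

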Efficacy Endpoint: Hyperglycemia					
	Duration (in minutes) and percentage of time with glucose values >180, 181-250 and >250 mg/dL [10.0, 10.1-13.9 and 13.9 mmol/L]	X	X	X	
Efficacy Endpoint: Daily CGM Data Summary					
	Mean sensor glucose	X	X	X	
	Median sensor glucose	X	X	X	
Efficacy Endpoint: Glucose Variability and Risk Assessment					
Within-Day	CV	X	X	X	
	SD	X	X	X	
	IQR	X	X	X	
Between-Day	CV	X	X	X	
	SD	X	X	X	
Overall ^e	CV	X	X	X	
	SD	X	X	X	
	IQR	X	X	X	

Efficacy Endpoint: Highest Postprandial Glucose					
	Time from start of meal to the highest postprandial glucose level (minutes) within 4 hours after meal(s)				X
	Highest postprandial glucose level within 4 hours after meal(s)				X
	Highest postprandial glucose excursion level within 4 hours after meal(s)				X
Safety Endpoint: Hypoglycemia ^f					
	Duration (in minutes) and percentage of time with sensor glucose values <54, 54-69 and <70 mg/dL [3.0, 3.0-3.8 and 3.9 mmol/L]	X	X	X	X

Abbreviations: AUC = area under curve; CGM = continuous glucose monitoring; CV = coefficient of variation; hr = hour; IQR = interquartile range; SD = Standard deviation.

- ^a Daytime: 0600 hours to midnight (06:00:00-23:59:59 on the 24-hour clock).
- ^b Nighttime: midnight to 0600 hours (00:00:00-05:59:59 on the 24-hour clock).
- ^c By meals: for morning (breakfast), midday (lunch) and evening (dinner) meals and overall (average across all meals). The start time of morning, midday and evening meals are determined as the first entry in the CGM data during [04:00:00, 11:00:00], (11:00:00, 15:00:00] and [17:00:00, 21:00:00], respectively. When calculating time in ranges (target, hypo, hyper) for meals (0 to 1 hour, 0 to 2 hours, 0 to 3 hours and 0 to 4 hours), any data that are collected after the next meal event will be excluded.
- ^d Mean sensor glucose measured at different time points (1, 2, 3 or 4 hours) after the start of the meal minus mean sensor glucose at the start of meal
- ^e Overall variability refers to the variability calculated based upon all the CGM measurements collected across all valid days for each derivation period
- ^f In addition, postprandial hypoglycemia during the following time interval after each meal and overall will also be derived: 0 to 1 hour, 0 to 2 hours, 2 to 4 hours, 0 to 4 hours. The calculation will exclude the data from patients who have had the next meal event before the end of time interval.

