9.2. Glucose in Target Ranges, Hypoglycemia or Hyperglycemia

Glucose in target range, hypoglycemia or hyperglycemia will be calculated as the average value of percentage of time within a glucose range (target, hypo- or hyperglycemia ranges) on all valid CGM days during that visit.

The percentage of time within a glucose range (target, hypo- or hyperglycemia ranges) will be calculated as the number of observations within the specified range divided by the number of observations in the time interval (eg, 24-hour period). The duration (in minutes) within the glucose range will then be calculated as the percentage of time within the glucose range times the length of the period (24 hour, 18 hour, and 6 hour, for the periods of 24-hour, daytime or nighttime, respectively).

For example, if a patient had a total of 15 observations with glucose values <70 mg/dL (3.9 mmol/L) out of a total of 288 observations recorded during the 24-hour period in a valid CGM day at Visit 3, the percentage of time spent in hypoglycemia during the 24-hour period for this patient at that valid CGM day at Visit 3 will be calculated as $15/288 = 5.2\%$. The duration (in minutes) with hypoglycemia (glucose value <70 mg/dL [3.9 mmol/L]) during the 24-hour period for this patient at that valid CGM day at Visit 3 will be calculated as the percentage times 1440, (ie, $15/288 * 1440 = 75.0$ minutes). Then derive the CGM outcome for each visit by averaging across all valid CGM days at that visit.

The percentage and duration in ranges within 0 to 1 hour, 0 to 2 hours, 0 to 3 hours, and 0 to 4 hours after meals will also be derived.

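### By-meal hypoglycemia at 0–1, 0–2 and 0–4 h falls under two unranked next-meal rules, and the exclusion is worded per patient instead of per meal window

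*SAP*

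**What the plan says.** The hypoglycemia row of SAP Table ITSZ.6.5 (Section 6.13) is marked as a by-meal measure, so footnote c applies. It also carries footnote f.

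- **Footnote c** covers time in target, hypo and hyper ranges after meals at 0–1, 0–2, 0–3 and 0–4 h. Its rule is truncation: "any data that are collected after the next meal event will be excluded". It also fixes meal starts as "the first entry in the CGM data during [04:00:00, 11:00:00], (11:00:00, 15:00:00] and [17:00:00, 21:00:00], respectively".
- **Footnote f** opens "In addition, postprandial hypoglycemia during the following time interval after each meal and overall will also be derived" and lists 0–1, 0–2, 2–4 and 0–4 h. Its rule is exclusion: "The calculation will exclude the data from patients who have had the next meal event before the end of time interval".
- **SAP Appendix 1, Section 9.2**, which derives time in ranges, says that percentage and duration "within 0 to 1 hour, 0 to 2 hours, 0 to 3 hours, and 0 to 4 hours after meals will also be derived". It gives no next-meal rule. It computes a percentage for each valid day and then averages over days.
- **SAP Appendix 1, Sections 9.8.1 and 9.8.2**, the footnote to SAP Table ITSZ.4.1 and the footnote to the objectives table in protocol Section 3 also exclude the data of patients or participants, here for highest PPG and time to highest PPG. Sections 9.8.1 and 9.8.2 leave out the limit that the next meal must come before the interval ends.

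**The concern.** Two faults are present.

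First, the same measure over the same window is given two rules. When a next meal falls inside the window, one rule keeps the earlier readings and the other discards the window. A programmer must choose, possibly after seeing data. The choice can be related to the outcome, because a low may be what prompts the next meal. Discarding the window can lose that low; truncating counts it over a shorter denominator.

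Second, the unit of exclusion is the person. Followed literally, a single early lunch would cost a participant all breakfast values in that period. This would reach postprandial hypoglycemia and also highest PPG and time to highest PPG, which are listed exploratory endpoints in a study that titrates to the post-prandial peak.

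**Working it through.** The documents give no figure for this issue, so the check sets the rules side by side and then works an example.

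**1. Which windows have two rules**

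| Window after meal | Footnote c (truncate) | Footnote f (exclude) | Rules |
|---|---|---|---|
| 0–1 h | yes | yes | two |
| 0–2 h | yes | yes | two |
| 0–3 h | yes | no | one |
| 2–4 h | no | yes | one |
| 0–4 h | yes | yes | two |

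**2. When the two rules can differ**

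- Meal starts under footnote c: lunch by 15:00 and dinner from 17:00, a gap of at least 120 min. Dinner by 21:00 and breakfast from 04:00, a gap of at least 7 h. With main meals only, 0–1 and 0–2 h can differ only after breakfast, and 0–4 h only after breakfast or lunch.
- Completeness rule (SAP 6.13): at least 70% of expected readings. The SAP's example of 24 readings for 2 h reproduces as 120 / 5 = 24, so 1 h has 12 and 4 h has 48.
- Assume that the 70% refers to the planned window. Then 0.7 × 12 = 8.4, so 9 readings (45 min); 0.7 × 24 = 16.8, so 17 readings (85 min); 0.7 × 48 = 33.6, so 34 readings (170 min). A window cut shorter than this fails under footnote c as well. The rules then differ only when the next meal comes about 45–60, 85–120 or 170–240 min after the meal start.

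**3. Example at participant level (assumed times)**

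Inputs: 10 valid days, as in Days 36 to 45; breakfast at 09:00; on one day lunch at 12:00, with six readings below 70 mg/dL before it; no other lows. Window: breakfast 0–4 h.

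- Readings before the next meal: 180 / 5 = 36, and 36 / 48 = 75%, so the day passes the 70% rule.
- Footnote c: 6 / 36 = 16.67% on that day; 10-day mean (16.67 + 9 × 0) / 10 = 1.67%.
- Footnote f applied per meal: that window is dropped; 9-day mean (9 × 0) / 9 = 0%.
- Footnote f as worded: the participant's breakfast data are dropped, so no value.
- For reference, a full window with no later lows would give 6 / 48 = 12.5% on that day and 1.25% as the 10-day mean.
- Averaged with equal weight over three meals, with no lows after the other two, footnote c gives 1.67 / 3 = 0.56%, against 0% under footnote f per meal.

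**4. What the literal unit would cost**

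The documents do not say how often a next meal falls inside the window. Take a chance p per meal as an assumption, independent across days, for one meal type over 10 days. Of the 30 evaluable participants (SAP 5.2), 30 × (1 − p)^10 keep a value in one period, and 30 × (1 − p)^20 in both baseline and endpoint, which SAP Table ITSZ.6.2 requires.

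| Assumed p | Left, one period | Left, both periods | Windows kept if excluded per meal |
|---|---|---|---|
| 2% | 24.5 | 20.0 | 98% |
| 5% | 18.0 | 10.8 | 95% |
| 10% | 10.5 | 3.6 | 90% |
| 20% | 3.2 | 0.3 | 80% |

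These counts describe the literal reading only. They do not predict what would be programmed.

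**The case against.** Four points can be made for the plan.

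- **Footnote f may be a separate derivation.** Its opening words suggest an addition to footnote c. That is possible, but the SAP would then produce two unlabelled results for the same measure and window, with neither named as the main one.
- **The meal was surely meant.** Footnote f speaks of an interval after each meal, and 9.2 works by day before averaging. This is the likely intent and it stands. It makes the patient wording an error to correct; it does not make the wording right. A reader might go further and infer that one early lunch removes all of a participant's windows, dinner included. The documents do not support that, because footnote f derives results after each meal as well as overall.
- **The late-low question has its own window.** A reader might infer that the conflict undermines the study's claim about late post-meal hypoglycemia. It does not: 2–4 h, the window most aimed at late lows, has a single rule and needs only the unit corrected. The 0–4 h window also reaches those lows and does carry the conflict.
- **The outputs are supplementary.** By-meal hypoglycemia is not a listed protocol endpoint; the listed one is time below 54 mg/dL without meal windows. Differences at 0–1 and 0–2 h need a late breakfast and a very early lunch. This stands and sets the severity. It does not cover the unit wording, which also governs the listed endpoints of highest PPG and time to highest PPG.

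**Conclusion.** The point holds as a minor SAP correction. The rule conflict is confined to hypoglycemia at 0–1, 0–2 and 0–4 h. The unit error is confined to postprandial hypoglycemia, highest PPG and time to highest PPG.

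A reader might infer that the primary analysis is affected. It is not: the primary endpoint and the 24-hour, daytime and nighttime measures use no next-meal rule, and the by-meal time in range mentioned in SAP 6.9.1 falls under footnote c alone.

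In the example the two rules differ by 1.67 percentage points in one participant's breakfast mean, and by 0.56 when averaged over three meals. This rests on assumed meal times, one early meal in 10 days, and the 70% rule being taken on the planned window. The effect in the trial cannot be sized, because the documents do not give the frequency of early next meals.

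**What to change.** 1. In footnote f, Sections 9.8.1 and 9.8.2 and the footnote to SAP Table ITSZ.4.1, make the meal window the unit, for example: *A meal window is left out if another meal event starts before that window ends.* State in the SAP that the protocol Section 3 footnote is applied in this way. Protocol Section 9.4 asks for an amendment only when a principal feature changes, and none does here.
2. State one next-meal rule for hypoglycemia at 0–1, 0–2 and 0–4 h in footnotes c and f, and repeat it in 9.2. If both derivations are wanted, label one as main and the other as sensitivity.
3. Report how many meal windows were excluded or truncated at baseline and at endpoint.

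The cost is SAP wording and one count table, plus a labelled sensitivity output if both rules are kept; no new data are needed. Each choice has a drawback. Complete windows leave fewer meals. Truncation gives noisier percentages that can run high when a low prompts the next meal.
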